Treatment Indication:	Autosomal Dominant Polycystic Kidney Disease (ADPKD)
Objective:	The primary objective of this trial is: 
 To evaluate and describe the long-term safety of tolvaptan.
Trial Design:	
This trial is a phase 3b, multi-center, open-label extension trial. Subjects will be eligible for screening into this trial if they:
 
 Completed and transferred from the double-blind Trial 156-13-210 (12-month period including post-treatment follow-up, regardless of whether this was on-treatment or off-treatment), or have completed all but the last follow-up visit, which will be combined with the first visit in this trial or Completed Trial 156-08-271 or a prior tolvaptan ADPKD trial, or have completed all but the end of trial visit, which will be combined with the first visit in this trial or Interrupted or discontinued treatment in a prior tolvaptan ADPKD trial (other than Trial 156-13-210). Subjects may be enrolled with medical monitor approval, and additional close monitoring may be required at the beginning of the trial 
For purposes of ensuring subject safety, all subjects will be monitored for hepatic safety monthly until they have accumulated 18 months of tolvaptan exposure. After that, and following the approval from the medical monitor, hepatic monitoring will be required every 3 months. If subjects

Confidential - Otsuka Proprietary Information

2

06 March 2015

Until the information herein is released by Otsuka to the public domain, the contents of this document are Otsuka confidential information and should not be duplicated or re-distributed without prior written consent of Otsuka.

Protocol 156-13-211

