After consenting, subjects will be assigned a new screening number. Subjects who are found to be eligible will retain the same subject number they had been assigned in their previous trial. For purposes of ensuring subject safety, tolvaptan exposure of at least 18 months is required for all subjects. While Trial 156-13-210 remains blinded, subjects enrolling from any prior trial besides Trial 156-08-271 are scheduled to have monthly hepatic monitoring for the first 18 months of this trial. After that, following the approval of the medical monitor, hepatic monitoring will take place every 3 months. Subjects enrolling from Trial 156-08-271 will have hepatic monitoring every 3 months. All Trial 156-13-210 subjects who are eligible for this trial will initially be scheduled to have trial visits and hepatic monitoring monthly for the first 18 months, then every 3 months thereafter, because their tolvaptan exposure cannot be determined since Trial 156-13-210 is a double blind trial. Once unblinding occurs, it can be determined which subjects received tolvaptan in Trial 156-13-210. These subjects may have their trial visits/hepatic transaminase monitoring changed to every 3 months sooner as their previous tolvaptan exposure in Trial 156-13-210 can count towards the 18-month threshold. Subjects from prior tolvaptan trials other than Trial 156-08-271 will have monthly trial visits/ALT level assessments for the first 18 months. After that, the trial visits/ALT monitoring will be conducted every 3 months after the change in frequency is confirmed with the medical monitor.

Enrollment in this trial will be closed when the last eligible subject from Trial 156-13-210 enrolls in this trial.

The duration of this trial is planned to continue

- Until the last subject from Trial 156-13-210 completes 18 months of tolvaptan treatment in this trial
- Subjects enrolling from other trials will conclude their participation once tolvaptan becomes available through routine prescription or through a CCI Trial 156-13-210 subjects may opt to conclude their participation in this trial if tolvaptan becomes available before they complete 18 months of treatment in this trial

Protocol 156-13-211

[figure not shown]

Figure 3.1-1 Trial Design Schematic

Protocol 156-13-211

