^eCentral laboratory non-fasting serum laboratory tests will be performed. All subjects must be monitored for hepatic safety monthly until they have known tolvaptan exposure data of at least 18 months. After that, and following the approval of the medical monitor, hepatic monitoring will take place every 3 months. Trial 156-13-210 subjects who are eligible for this trial will have trial visits/hepatic monitoring monthly for the first 18 months of this trial then every 3 months thereafter, because their tolvaptan exposure will be unknown. Once unblinding occurs, it can be determined which subjects received tolvaptan in Trial 156-13-210. These subjects may have their trial visits/hepatic transaminase monitoring changed to every 3 months sooner as their previous tolvaptan exposure in Trial 156-13-210 can count towards the 18 month threshold. Subjects who enroll from other ADPKD tolvaptan trials will be monitored for hepatic safely monthly for their first 18 months they are in this trial.

^fHepatitis testing at screening will be optional. If hepatitis testing is performed, then both pre- and post-counseling activities relating to hepatitis testing are to be carried out based on local requirements and best practices. Upon request, if clinically indicated and approved by the medical monitor, subjects may have the following evaluations in addition to the protocol-specified chemistry panel: serum calcium, phosphorous, parathyroid hormone, vitamin D, and bicarbonate levels.

^gA full liver function panel (AST, ALT, alkaline phosphatase, BT) will be done at screening. All other liver function tests at subsequent visits are for ALT only, unless otherwise clinically indicated. An ALT elevation > 2 × ULN should trigger prompt testing of hepatic function within 72 hours. Any transaminase or bilirubin values which exceed 2 × ULN should prompt immediate retesting within 72 hours. While values remain in an abnormal range, testing frequency should be increased to at least weekly for the first month, gradually returning to monthly, and every 3 months as indicated by the results. Local liver function panel analyses will also be performed more frequently, if necessary.

^hUrine osmolality is optional.

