3.7.1.3 Monthly Visit (± 7 days)

The following subjects will return for a monthly visit to assess safety and tolerability of IMP and to monitor liver function.

- Subjects enrolling from the double-blind Trial 156-13-210 will have monthly trial visits/ALT level assessments for the first 18 months while treatment code from Trial 156-13-210 remains blinded, to ensure that they have adequate safety monitoring during this period of susceptibility. Once unblinding occurs, it can be determined which subjects received tolvaptan in Trial 156-13-210. These subjects may have their trial visits/hepatic transaminase monitoring change to every 3 months sooner as their previous tolvaptan exposure in Trial 156-13-210

Protocol 156-13-211

can count towards the 18-month threshold. The investigator will need to discuss the change in frequency with the medical monitor before instituting the change.

- Subjects from prior tolvaptan trials other than Trial 156-08-271 will have monthly trial visits/ALT level assessments for the first 18 months. After that, the trial visits/ALT monitoring will be conducted every 3 months after the change in frequency is confirmed with the medical monitor.
- Subjects enrolling from the open-label Trial 156-08-271 who have greater than 18 months of exposure to tolvaptan will have trial visits/ALT monitoring conducted every 3 months.

The following will be assessments will be completed:

1. Review dietary recommendations and compliance.

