3.7.2.4 Assessment of Liver Symptoms, Signs or Test Abnormalities

Testing for hepatic transaminase (ALT/AST), alkaline phosphatase, bilirubin direct, and BT will be performed during screening. Subjects enrolling from the double-blind Trial 156-13-210 will have monthly ALT assessments for the first 18 months while the treatment code from Trial 156-13-210 remains blinded to ensure that all subjects have adequate safety monitoring during this period of susceptibility. Once unblinding occurs, it can be determined which subjects received tolvaptan in Trial 156-13-210. These subjects may have their trial visits/hepatic transaminase monitoring changed to every 3 months sooner as their previous tolvaptan exposure in Trial 156-13-210 can count towards the 18-month threshold.

Protocol 156-13-211

Following the first 18 months, ALT assessments will be made every 3 months for Trial 156-13-210 subjects and for subjects from other tolvaptan ADPKD trials besides Trial 156-08-271.

Subjects enrolling from the open-label Trial 156-08-271 who have tolvaptan exposure greater than 18 months will continue with ALT monitoring every 3 months.

Subjects enrolling from prior tolvaptan trials besides Trial 156-08-271 will have monthly ALT assessments for the first 18 months. Upon reaching 18 months of exposure and after confirmation from the medical monitor, the frequency of ALT monitoring for these subjects will occur every 3 months.

ALT will also be assessed at the Early Termination/EoTx visit and at the 7-day Follow-up visit.

Management of liver abnormalities is discussed in the paragraphs below.

3.7.2.4.1 Liver Test Abnormalities and Interruption/Discontinuation of Investigational Medicinal Product

An ALT elevation $2 \times$ ULN or the appearance of any suspicious symptom or sign should trigger prompt testing of hepatic function (ie, within 72 hours). Local laboratory testing is acceptable, ideally with a concurrent central laboratory sample for confirmation.

Any transaminase or bilirubin values which exceed $2 \times$ ULN should also prompt immediate retesting within 72 hours. While values remain in an abnormal range, testing frequency should be increased to at least weekly for the first month, gradually returning to monthly, or every three months as indicated by the results.

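### Protocol 3.1 puts Trial 156-08-271 entrants on 3-monthly liver monitoring with no exposure condition, which conflicts with the plan's own monthly-until-18-months rule for any such entrant below 18 months of tolvaptan

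*Protocol*

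**What the plan says.** Section 3.1 of the protocol sets the schedule by source trial: "Subjects enrolling from Trial 156-08-271 will have hepatic monitoring every 3 months". Shortly before that, it defines the monthly group so as to leave these subjects out: "subjects enrolling from any prior trial besides Trial 156-08-271 are scheduled to have monthly hepatic monitoring for the first 18 months of this trial". The UK version of 3.1 and SAP 3.1 carry the same sentences.

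Two other places set the schedule by exposure and cover everyone:

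- Synopsis, Trial Design: "all subjects will be monitored for hepatic safety monthly until they have accumulated 18 months of tolvaptan exposure". After that, "following the approval from the medical monitor, hepatic monitoring will be required every 3 months".
- Table 3.7-1, footnote e: "All subjects must be monitored for hepatic safety monthly until they have known tolvaptan exposure data of at least 18 months". Footnote b likewise assigns visit frequency by time on tolvaptan, with the cut at 18 months.

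Other sections bear on the same subjects:

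- Section 1.3 justifies the 3-monthly schedule for 271 entrants by saying that they will already have had 18 months or more of the drug.
- Section 3.7.1.3 adds the condition that 3.1 lacks: "Subjects enrolling from the open-label Trial 156-08-271 who have greater than 18 months of exposure to tolvaptan will have trial visits/ALT monitoring" at 3-month intervals. Section 3.7.2.4 has the same condition, but its monthly group again leaves Trial 271 out: "Subjects enrolling from prior tolvaptan trials besides Trial 156-08-271 will have monthly ALT assessments for the first 18 months".
- Section 3.7.2.2 lists 271 entrants under 3-monthly ALT. It is unclear whether the 18-month qualifier earlier in that sentence applies to them.
- Criterion 1 of Table 3.4.2-1 admits subjects who interrupted or discontinued treatment in any tolvaptan trial except 156-13-210, with medical monitor approval and no minimum exposure.

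**The concern.** One rule goes by where the subject came from, the other by how long the subject has taken tolvaptan. They part company for a 271 entrant below 18 months. Section 3.1 tells the site to test such a subject every 3 months; the synopsis and footnote e say monthly. Sections 3.7.1.3 and 3.7.2.4 do not settle it, because the subject fits neither their monthly group nor their 3-monthly group.

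This matters because section 2.1 locates the excess of transaminase elevations and drug-induced liver injury in the first 18 months. It reports ALT above 3 times ULN in 4.4% on tolvaptan against 1% on placebo over 3 years, and names frequent testing as the means of catching injury early. A subject handled as 3.1 reads would have sparse testing in the period for which monthly testing was designed.

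**Working it through.** The plan gives no figure to reproduce here. The check has two parts.

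**1. What each section requires of a 271 entrant**

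| Source | At or past 18 months | Below 18 months |
|---|---|---|
| Protocol 3.1, UK 3.1, SAP 3.1 | 3-monthly | 3-monthly |
| Synopsis; Table 3.7-1 footnotes b and e | 3-monthly | monthly |
| 3.7.1.3 and 3.7.2.4 | 3-monthly | not placed |
| 3.7.2.2 | 3-monthly | ambiguous |
| 1.3 | 3-monthly | presumed not to exist |

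The conflict is confined to the right-hand column.

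Can anyone be in that column? Section 3.1 also says "tolvaptan exposure of at least 18 months is required for all subjects". This cannot be an entry requirement, because Trial 156-13-210 placebo subjects have no exposure from that trial and are enrolled. It is best read as the same 18-month monitoring threshold. No eligibility criterion sets a minimum exposure, so a 271 interrupter or discontinuer below 18 months is admissible.

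**2. Size of the difference for one affected subject**

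Inputs: visit windows of ±7 days (monthly) and ±14 days (3-monthly) from Table 3.7-1; one month = 365.25/12 = 30.4 days, three months = 91.3 days. Prior exposure e is not given, so 6, 12 and 15 months are assumed.

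- Longest gap between scheduled ALT tests: 30.4 + 14 = 44 days monthly; 91.3 + 28 = 119 days 3-monthly.
- Latest first scheduled on-treatment ALT: 30.4 + 7 = day 37; 91.3 + 14 = day 105.
- ALT draws from entry to 18 months of exposure: 18 − e monthly; (18 − e)/3 3-monthly.

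| Assumed e (months) | Monthly | 3-monthly | Difference |
|---|---|---|---|
| 6 | 12 | 4 | 8 |
| 12 | 6 | 2 | 4 |
| 15 | 3 | 1 | 2 |
| 18 or more | no difference | | 0 |

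**SAP windows.** If the subject is instead tested monthly as footnote e requires, SAP 3.4 still maps all hepatic data of 271 subjects with Table 3.4.2 and keeps the last value per window. Monthly visits 1 to 12 fall on about days 31, 62, 92, 123, 153, 184, 214, 245, 275, 305, 336 and 366. The windows 2–137, 138–229, 230–320 and 321–412 then hold visits 1–4, 5–7, 8–10 and 11–12. By-window summaries would keep 4 of 12 values (e = 6), 2 of 6 (e = 12) or 1 of 3 (e = 15). Under Table 3.4.1 each visit has its own window.

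**The case against.** The strongest reply is that the protective rule is already there, more than once. Footnote e is mandatory in tone, footnote b and the synopsis agree with it, and 3.7.1.3 and 3.7.2.4 limit 3-monthly tests for 271 entrants to those above 18 months. Table 3.7-1 is the operational schedule and 3.1 is a design overview. The one identified entry route needs medical monitor approval, and an interrupter may have had years of exposure. Exclusion criterion 6 removes subjects with prior significant tolvaptan-related liver injury. Suspicious symptoms or ALT above 2 times ULN trigger testing within 72 hours.

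Most of this stands, and it limits the risk. It does not close the gap. Closer monitoring on the interrupted/discontinued route is optional under criterion 1. The ALT trigger works only once a test has been taken. Three copies of 3.1 still give an instruction that differs from the schedule table.

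A reader might infer more than the documents support:

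- *That 3.1 contradicts the general rule for the whole 271 cohort.* It does not; the frequencies coincide from 18 months on.
- *That affected subjects would be sent home with 3 months of drug instead of 1.* Section 3.7.1.2 dispenses according to the required visit schedule, which footnote e makes monthly below 18 months. The larger supply follows only if the schedule has already been misapplied.
- *That the SAP would lose liver signals.* The thinning affects by-window summaries only, and it requires monthly testing, so it cannot occur together with the under-testing at the same visits. SAP 8 bases its summaries on all available data, and its liver variables include threshold frequencies, times to onset and peak, and Hy's criteria. SAP 8.2 is incomplete in the public text, so no loss can be shown there.

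**Conclusion.** The inconsistency is real but narrow. For a 271 entrant with less than 18 months of tolvaptan, 3.1 and its copies call for 3-monthly tests while the synopsis and Table 3.7-1 call for monthly ones, and no section resolves the difference for that subject. Entry rules admit such a subject. How many there are is not stated, and it may be none.

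Per affected subject, following 3.1 would mean about a third of the scheduled ALT tests up to 18 months. The draw counts rest on assumed prior exposures of 6 to 15 months, and the 119-day and 44-day gaps are extremes of the visit windows, not typical intervals. Sample size and error rates are not involved. The correction is worth making because it brings 3.1 into line with the sponsor's own rule for all subjects.

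**What to change.** In section 3.1 of both protocol versions and in SAP 3.1, replace the sentence with:

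> Trial 156-08-271 entrants with at least 18 months of documented tolvaptan exposure are monitored for hepatic safety every 3 months; those with less are monitored monthly until they reach 18 months.

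Add the same monthly clause in 3.7.1.3, 3.7.2.2 and 3.7.2.4. Do not add a medical monitor approval step for 271 entrants already past 18 months, because 3.7.2.4 has them simply continue 3-monthly.

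As a minor consequential edit, state in SAP 3.4 that hepatic data of any 271 entrant on monthly monitoring are mapped with Table 3.4.1, and adjust that table's title and the text introducing both tables to match.

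Cost: wording edits in both protocol versions, which section 13 requires to go to the IRB/IEC as an amendment, plus two places in the SAP. For subjects, the cost is about 8, 4 or 2 extra ALT visits at an assumed 6, 12 or 15 months of prior exposure. Test frequency is unchanged for 271 entrants at or past 18 months.

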3.2 Treatments

The dose regimens to be used in this trial are 15/15 mg, 30/15 mg, 45/15 mg, 60/30 mg, and 90/30 mg.

Following consent, and once subjects have satisfied all of the inclusion criteria and none of the exclusion criteria, subjects will retain the subject number assigned from their previous trial. Subjects will receive open-label tolvaptan for the duration of the trial. All subjects will be administered tolvaptan tablets in a daily split-dose, once upon awakening and another approximately 8 to 9 hours later (twice daily dosing). The exact time of dosing may be adjusted based on wake/sleep habits (eg, standard 8 AM and 5 PM may be switched to 10 PM and 7 AM if working a night shift). However, dosing times should be consistent for each individual's daily dose to maximize receptor suppression. Doses will be recorded as early dose/late dose (eg, 60/30 mg).

A subject's starting dose in this trial will be dependent on the trial in which they were previously enrolled:

- **156-13-210-** initiated on tolvaptan at a split-dose of 45/15 mg with upward titration every 3 to 4 days to 60/30 mg or 90/30 mg per day according to tolerability
- **156-08-271-** will retain the last dose level from 271 and start at the same dose in this trial
- **Prior tolvaptan trials-** initiated on tolvaptan at a split-dose of 45/15 mg with upward titration every 3 to 4 days to 60/30 mg or 90/30 mg per day according to tolerability

Down titration to 30/15 mg and 15/15 mg is also permitted at the discretion of the investigator according to subject tolerability with medical monitor notification. Further down titration to 30 or 15 mg once daily may be allowed only for metabolic drug-drug interaction and requires medical monitor approval.

Protocol 156-13-211

Table 3.2-1 Trial Treatments		
Trial Day	Time	Dose
Day 1 to last on-treatment visit	8:00 am	1 to 6 tolvaptan tablets (15 mg or 30 mg each)
	4:00 to 5:00 pm	1 to 2 tolvaptan tablets (15 mg or 30 mg each) Allowed doses are 45/15 mg, 60/30 mg, 90/30 mg. Down titration to 30/15 mg and 15/15 mg will be allowed after discussion with the medical monitor. Further down titration to 30 or 15 mg once daily may be allowed only for metabolic drug-drug interaction and requires medical monitor approval.

For subjects moving from the 156-13-210 trial and requiring tolvaptan titration, it will be conducted in the following way: subjects will be instructed to take tolvaptan starting at a split dose of 45/15 mg (as 3 tablets upon waking and 1 tablet approximately 8 to 9 hours later) and to titrate up every 3 to 4 days; first to 60/30 mg, then up to the maximum dose of 90/30 mg. Titration will be accomplished by increasing the number of tablets/dose and/or switching from 15 mg tablets to 30 mg tablets. Prior to each upward titration, the subject's tolerability to the current dose will be assessed by asking, "Could you tolerate this dose of trial medication for the rest of your life?" Subjects will continue in the trial with the regimen to which tolerability was established.

While taking tolvaptan, all subjects should be instructed to ingest fluids in anticipation of, or at the first sign of thirst in order to avoid excessive thirst or dehydration. Additionally, subjects should ingest 1 to 2 cups of water before bedtime regardless of perceived thirst and replenish fluids overnight with each episode of nocturia.

3.2.1 Dosing with CYP3A4 Potent Inhibitors

Tolvaptan is a sensitive CYP3A4 substrate with 4-fold or higher increases in exposure following administration with potent CYP3A4 inhibitors.⁴

For subjects requiring treatment with a potent CYP3A4 inhibitor and on a total daily tolvaptan dose of 90 or 120 mg, tolvaptan treatment should be reduced to 30 mg once daily. The dose may be reduced to 15 mg once daily for tolerability. For subjects on a total daily dose of 60 mg, tolvaptan treatment should be reduced to 15 mg once daily. For subjects on lower total daily doses, tolvaptan interruption should be considered if no alternative medications can be used.

Protocol 156-13-211

3.2.2 Dosing with CYP3A4 Moderate Inhibitors

For subjects who require dosing with a moderate inhibitor, initial tolvaptan reductions as shown below should be tried, with further dose reductions or interruption as necessary for tolerability.

- 90/30 mg to 45/15 mg
- 60/30 mg to 30/15 mg
- 45/15 mg to 15/15 mg
- 30/15 mg to 15 mg once daily
- 15/15 mg to 15 mg once daily

A partial list of strong and moderate CYP3A4 inhibitors can be found in [Section 4.1](#).

3.3 Trial Population

This trial will include approximately 2,500 subjects over the age of 18 years with ADPKD diagnosed by Pei-Ravine criteria^{11 12} (modified by magnetic resonance imaging [MRI]) who completed or participated in a prior tolvaptan trial.

3.4 Eligibility Criteria

3.4.1 Informed Consent

Each investigator has both ethical and legal responsibility to ensure that subjects being considered for inclusion in this trial are given a full explanation of the protocol and of their role and responsibilities in the proposed research. This shall be documented on a written informed consent form (ICF) that shall be approved by the same institutional review board/independent ethics committee (IRB/IEC) responsible for approval of this protocol. Each ICF will comply with the International Conference on Harmonisation (ICH) Good Clinical Practice (GCP) Guideline¹⁴ and local regulatory requirements, and must adhere to the ethical principles that have their origin in the Declaration of Helsinki. The investigator agrees to obtain sponsor approval of any written ICF used in the trial prior to submission to the IRB/IEC.

Investigators may discuss trial availability and the possibility for entry with a potential subject without first obtaining consent. However, informed consent will be obtained from all subjects (or their guardian or legal representative) and documented prior to initiation of any procedures that are performed solely for the purpose of determining eligibility for this trial, including withdrawal from current medication(s).

Protocol 156-13-211

Once appropriate essential information has been provided and fully explained in layman’s language to the subject by the investigator (or a qualified designee), the IRB/IEC-approved written ICF will be signed and dated by both the subject and the person obtaining consent (investigator or designee), as well as by any other parties required by the IRB/IEC. The subject will receive a copy of the signed ICF; the original shall be kept on file by the investigator.

CCI
 [Redacted text block]

